Adherence, or "sticking to your diet" is important for successful initial weight loss and keeping off the weight over the long term (1). While early behavioral and dietary adherence have been associated with greater weight loss, sticking to a diet plan is difficult. It is not clear if adherence to any diet plan (even one which does not produce weight loss) is hard or whether people who are overweight have more difficulty with adhering to diet plans compared to people who are relatively lean.

The main aim of this study is to evaluate dietary adherence in 3 groups of individuals participating in a 6-week heart-healthy dietary intervention program. Two groups [1. Lean (BMI < 25 kg/m²) and 2. Obese (BMI ≥ 30 kg/m²)] will receive a heart-healthy diet designed to maintain their weight, and the third group [3. Obese] will be given a heart-healthy diet that is 35% *less* than their daily calorie needs to lose weight. Participants will attend one counseling session per week and will be contacted randomly 1x/week by study staff for completion of a 24-hour dietary recall. They will complete daily food diaries and daily records using smart-phones. Prior to starting the assigned heart-healthy dietary intervention, participants will complete questionnaires that include questions about how motivated they are to follow a diet, lose weight, and change eating patterns. These findings may help us understand what factors affect adherence, and help us design weight loss studies that improve people's ability to stick to diet interventions.

A. INTRODUCTION

Obesity, defined by the NHLBI in 1998 (2) as a body mass index [BMI, in kg/m^2] > 30 , has become a medical epidemic in the US (3), and is reaching pandemic proportions in most industrialized countries. Obesity is linked to a number of medical complications and is a leading cause of preventable death in America, contributing to over 150,000 excess deaths per year (4). At any given time of the year, between 15 and 35% of the adult population in the US is reportedly attempting to lose weight (5), yet, successful weight reduction and maintenance of weight loss remain elusive goals for many dieters. In fact, a relatively small maximum average weight loss is common even in very low calorie long-term treatments (6). This low treatment efficacy has been consistently observed, and while some do achieve weight loss success, only about 20% of overweight individuals maintain the weight loss (7).

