Adherence is essential for initial weight loss and long-term weight maintenance. It is unclear whether adherence to dietary protocols differs between lean and obese individuals and whether non-adherence is specific to weight loss intervention diets (compared to weight maintenance diets). Several predictors of adherence to medical treatments have been described, including associations with memory, problem solving, neuropsychological factors, personality traits and levels of motivation. To understand how adherence may differ by adiposity and diet, we will examine differences in dietary adherence between lean and obese individuals and within the obese group between those prescribed a heart-healthy weight maintenance versus reduced calorie

diet. We will also examine predictors of adherence and the relationship between dietary adherence and weight loss.

B. AIMS

The primary goal of the current study is to determine whether or not there are differences in dietary adherence between lean and obese individuals and between two groups of obese individuals assigned different heart-healthy dietary prescriptions (weight maintaining diet [WMEN] vs. underfeeding [UF]). Thus 3 groups will be compared:

1. Lean WMEN
2. Obese WMEN
3. Obese UF

The secondary aim is to:

1. Examine predictors of adherence in general (e.g. motivation, self-efficacy, social support, personality traits, stress, neuropsychological/cognitive factors)

C. HYPOTHESES

The primary hypothesis for the study is that:

1. Adherence to a heart-healthy dietary intervention will be greatest in the lean WMEN group, followed by the WMEN obese group, and subsequently lowest in the UF obese group

The secondary hypotheses are that:

1. Within the UF group, individuals with higher adherence scores will lose more weight than those with lower scores

2. Poor performance on neuropsychological tests and problem solving questionnaires will be associated with decreased adherence across all groups
3. Higher levels of neuroticism will be associated with lower levels of dietary adherence in all 3 groups
4. Higher levels of motivation and self-efficacy will predict greater adherence

D. RESEARCH DESIGN & METHODS:

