Study Design: This is a study of lean and obese individuals undergoing a 6-week heart-healthy dietary intervention to examine dietary adherence. This design will allow us to determine whether or not levels of adherence are different between lean and obese individuals as well as between obese individuals receiving weight maintenance energy needs and those being underfed. Findings will also help us determine factors that influence dietary adherence.

1. Subjects and Recruitment: Non-diabetic individuals aged 18-70 years who are in good health and living in the greater Phoenix, AZ, metropolitan area are eligible to participate in this study. All subjects will be fully informed of the methods and risks of the study prior to giving written informed consent. Consent will be obtained by the principal investigator, co-investigators, study physicians or physician assistant, who will be well informed about the protocol and the intervention. Subjects will also be specifically advised that the results of testing for drug usage will be filed in the medical record and would, therefore, be available as part of this record. We do not plan or anticipate the enrollment of non-English speaking subjects; however they are not excluded from participation either. Should a non-English speaking subject be eligible for enrollment, IRB approval will be obtained for use of the short form consent

process in the absence of a fully translated consent document as outlined in SOP 12.9.1, under the provisions of 45 CFR 46.117(b)(2). IRB approval will be obtained according to IRB guidance prior to obtaining informed consent from the potential study participant/s.

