- Go/No Go Task (45): to examine inhibitory control. Subjects are required to press a key whenever a target stimulus is presented and to refrain from pressing the key when a non-target stimulus is presented
 - Meeting with study counselor: The counselor will review the weight-maintenance heart-healthy dietary prescription and provide the volunteer with 3 days of food. The volunteer will be instructed to eat only the foods provided, consume no additional foods, maintain their current levels of physical activity, and to keep track on a self-monitoring food record form.
 - Weight Maintenance Dietary Prescriptions:
 - Recent studies have found that using free prepared meals facilitated greater adherence (16) and weight loss compared with a control group (17). Therefore, because the primary aim of our study is to compare differences between lean and obese groups and WMEN versus UF diets (rather than investigate real-world learning), all food items will be provided by the CRU, primarily as prepackaged meals and snacks for the volunteers to take home (see Table 2 for sample menu).
 - All diets will have 20%, 30%, and 50% of daily calories provided as protein, fat and carbohydrate, respectively. They are designated as "heart-healthy" because they will be balanced diets, which are also low in cholesterol and saturated fat.
 - During the baseline week, all participants will be fed their weight maintaining energy needs (WMEN), equal to the number of calories calculated for each participant based on the WHO equation with an activity factor (1.3-1.5)(46;47), based on results from the PAR questionnaire.

- *Women:* 18 to 30 y: $EE = 13.3 \times \text{weight (kg)} + 344 \times \text{height (m)} + 35$
30 to 60 y: $EE = 8.7 \times \text{weight (kg)} - 25 \times \text{height (m)} + 865$
- *Men:* 18 to 30 y: $EE = 15.4 \times \text{weight (kg)} - 27 \times \text{height (m)} + 717$
30 to 60 y: $EE = 11.3 \times \text{weight (kg)} + 16 \times \text{height (m)} + 901$
- During the first week, and prior to randomization, all patients will come for 2 outpatient visits to be weighed
- If their weight changes by 2%, their caloric intake will be adjusted by 200 kcal accordingly

Baseline Visit 2:

1. Weight
2. Adjust calories by 2%, if needed

Outpatient Visits (6 weeks):

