- *Randomization:* During the first outpatient study visit, participants will meet with a study counselor to discuss randomization assignment. They will be provided with 4 days of food and will again be instructed to eat only the foods provided, consume no additional foods, maintain their current levels of physical activity, and to keep track on a self-monitoring food record form. Additionally, they will be instructed on how to use the smart-phone system
 - Heart-Healthy Dietary Prescriptions:
 - Both the lean and obese WMEN groups will continue to eat the same number of calories that were calculated for them during the baseline weight maintenance period

- The obese UF group will be assigned a diet of 35% of the calculated energy needs
- *Weight and BP*: obtained at each visit
- *Meal pick-up*: meals will be prepared by the metabolic kitchen and picked up on a twice weekly basis
- *Meeting with Study Counselor*: Participants will meet 1x/week with a study counselor to review food records and dietary adherence. The counselor will rate the participants adherence and participant will rate his/her adherence to the dietary prescription and to behavioral aspects on a 5- point Likert Scale (0 = low; 5 = high). Counselors will also obtain a rating of subjective hunger over the last week on the same Likert Scale (0 = low; 5 = high) and assess change in physical activity. Sessions will last 15-30 minutes.
- *Assessment of Adherence*: Subjects will complete additional assessments of adherence:
 - 24-hour recall: this will be conducted by a member of the study staff other than the primary counselor to avoid bias
 - Computerized confessional: participants will complete a computerized battery of questions that will include a 24-hour recall with prompts to encourage recall of various foods possibly consumed at various times during the day. Questions about other weight and eating behaviors will be included. Data from this procedure will enable us to compare with the in-person interview version of the 24-h recall and assess reliability

Outpatient Adherence Contacts:

- 24-h recall by phone: a member of the study staff will call at a random time, 1x/week to conduct a 24-h food recall

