8.3.a Radiation exposure due to DXA: The DXA scans will take place on the GE Lunar iDXA machine. The radiation exposure for a 188 mA scan may be as much as 1 mrem as indicated by a January 2014 internal radiation exposure review. According to the manufacturer, the medium and fast scan speeds are likely to result in one-half the radiation exposure of the slow scan speed. A typical radiation dosage from this procedure is equivalent to 1.22 days (iDXA) of exposure to natural background sources, such as the sun and outer space, or radioactive materials found naturally within the earth's air and soil. For subjects who move excessively during the scans, a complete or partial repeat of the scan procedure may be necessary. Thus, subjects could receive a maximum of 2 mrem (iDXA, 2.5 days of exposure) if the slow scanning mode is used each time. Participants in this study will undergo 2 DXA scans over the study period therefore the maximum amount of radiation they will receive in the first year could be as high as 4 mrem (iDXA, 5 days of exposure). This exposure increases the percent cancer risk from 25 percent to 25.00016 (iDXA). This is well within the NIH Phoenix Radiation Safety Guidelines for research subjects of 3,000 mrem in a 13-week period and 5,000 mrem per year. A urine pregnancy test will be performed in all females who are able to become pregnant prior to each DXA scan.

8.3.e Dietary Intervention: The side-effects of consuming a pre-selected diet are minimal and might include boredom, lack of desire to eat the prescribed foods and/or increased feelings of hunger.

8.3.e Questionnaires and computer performance tests: There are no known risks associated with completing any of these questionnaires. However, some of the questions may be of a highly personal nature; thus, subjects will be informed that they do not have to respond to all the questions if they choose not to do so. If this is the case, notations to that effect will be noted in the patient's record.

8.3.f Urine Drug Screen: Results of this test will be used only to determine study eligibility. If the result is positive, patients will be confidentially informed of the results and a recommendation for follow-up will be made with their primary physician.

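### The underfeeding diet is specified as 35% of energy needs in the methods but as 35% less than needs in the summary, a 1.86-fold difference in calories

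*Combined protocol and SAP*

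**What the plan says.** The opening summary of the combined protocol and SAP describes three groups. The third, obese and underfed, "will be given a heart-healthy diet that is 35% *less* than their daily calorie needs to lose weight". The emphasis on the word *less* is in the protocol.

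Section D.4 (Outpatient Visits, Heart-Healthy Dietary Prescriptions) sets the diets for the six intervention weeks. Both weight-maintenance (WMEN) groups stay on their baseline calories. For the third group it says: "The obese UF group will be assigned a diet of 35% of the calculated energy needs".

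These are the only two places in the available text that give a percentage. Elsewhere the UF diet is described in words only. For example, the summary before section B frames the comparison as "within the obese group between those prescribed a heart-healthy weight maintenance versus reduced calorie" diets. The risk statement in section 8.3.e begins: "The side-effects of consuming a pre-selected diet are minimal and might include boredom". It goes on to lack of desire for the food and increased hunger.

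The base for the percentage is each participant's WMEN, set in section D.4 (Weight Maintenance Dietary Prescriptions) from the WHO equation times an activity factor of 1.3 to 1.5. All food is supplied, and participants are told to eat nothing else.

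**The concern.** A diet that is 35% of needs is a 65% cut; a diet 35% below needs is a 35% cut. The protocol states both for the same group. The issue is this contradiction, not the choice of deficit.

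It matters because of where the doubtful figure stands. Obese WMEN versus obese UF is the randomised contrast, and the UF fraction is its dose. The D.4 sentence is the methods statement of that dose and sits next to the meal pick-up item. Since the unit provides all the food, the fraction applied fixes the prescribed intake.

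Three things are at stake:

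- **Delivery and safety.** The literal methods text is the more severe of the two. No calorie floor is stated, and section 8.3.e carries no precaution for very low intake.
- **Interpretation of adherence.** Six of the 21 weekly adherence points reward eating no extra food: one each from diary, interview, computerised recall and telephone recall, and two from EMA. How hard those points are to earn plausibly depends on the size of the deficit.
- **Weight loss and reproducibility.** The first secondary hypothesis concerns weight loss within UF. A reader who cannot tell a 35% from a 65% deficit cannot interpret or repeat the result.

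**Working it through.** **Inputs from the protocol**

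- Methods (D.4, Heart-Healthy Dietary Prescriptions), read literally: UF intake = 0.35 × WMEN.
- Opening summary: UF intake = (1 − 0.35) × WMEN = 0.65 × WMEN.
- WMEN = EE × activity factor, with factor 1.3 to 1.5 (D.4, Weight Maintenance Dietary Prescriptions).
- EE, women 30–60 y: 8.7 × kg − 25 × m + 865.
- EE, men 30–60 y: 11.3 × kg + 16 × m + 901.

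The plan prints no kcal figure for the UF diet, so there is none to reproduce.

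**Step 1: the ratio, which needs no assumptions.** Summary intake over literal methods intake = 0.65/0.35 = 1.86. The inverse is 0.35/0.65 = 0.54. The deficits differ by the same factor, 65%/35% = 1.86. The gap is 0.65 − 0.35 = 30% of WMEN. None of this depends on body size.

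**Step 2: illustration in kcal.** The heights and BMI values are assumptions; the documents do not give them.

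*Woman, 1.63 m, BMI 35.* Weight = 35 × 1.63² = 93.0 kg. EE = 8.7 × 93.0 − 25 × 1.63 + 865 = 1,633. WMEN = 1,633 × 1.3 to 1,633 × 1.5 = 2,123 to 2,450 kcal/d.

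*Man, 1.77 m, BMI 35.* Weight = 35 × 1.77² = 109.7 kg. EE = 11.3 × 109.7 + 16 × 1.77 + 901 = 2,168. WMEN = 2,819 to 3,253 kcal/d (before rounding of EE).

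| Assumed participant | WMEN (kcal/d) | Summary, 65% | Methods, 35% | Gap, 30% |
|---|---|---|---|---|
| Woman, BMI 35 | 2,123–2,450 | 1,380–1,592 | 743–857 | 637–735 |
| Man, BMI 35 | 2,819–3,253 | 1,832–2,114 | 987–1,138 | 846–976 |

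**Step 3: range.** At the same heights, the low end is a woman of BMI 30 at factor 1.3: WMEN 1,973, so 1,282 versus 691 kcal/d. The high end is a man of BMI 40 at factor 1.5: WMEN 3,518, so 2,287 versus 1,231 kcal/d.

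**Step 4: does the power calculation depend on the fraction?** No. Tables 3A and 3B use group means, SD 6, alpha 0.05 and n per group. For means 13/16/19 and n = 20, the noncentrality is 20 × (9 + 0 + 9)/36 = 10 on 2 and 57 df, and power is 0.793. For 13/16.5/20 it is 20 × (12.25 + 0 + 12.25)/36 = 13.6, and power is 0.906. Both match the protocol, and the diet fraction enters neither.

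**Step 5: which value was intended?** The summary's emphasised *less* is the only direct evidence, and it points to 65% of needs. The mild risk text in 8.3.e is weak indirect support, since it describes the diets of all three groups together. The phrase *reduced calorie* fits either reading.

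**The case against.** The strongest reply is that this is a slip of one word with no demonstrated effect. The randomised comparison stays valid under any fraction applied consistently. The adherence scoring rules do not mention the fraction, and sample size and analysis do not change. Harm arises only if staff apply the literal text despite the summary, and no kitchen instruction or diet order is available to show that they would. The consent form was not available either and may state the right figure.

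There are also safeguards: weight and blood pressure at each of two visits a week, weekly counselling with a hunger rating, withdrawal criteria (section 5.1), and evaluation of any adverse effect by a provider (section 8.2).

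Much of this stands. The harm is conditional on literal implementation, the statistical validity of the contrast is not in question, and the evidence for 65% rests mainly on one sentence. But monitoring acts only after participants have been on the wrong diet. The reply also offers no reason to leave the conflict in place. If 65% of needs was meant, the methods are wrong; if 35% was meant, the summary is wrong and the risk section needs rewriting.

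**Conclusion.** The concern holds. The protocol states the dose of the UF intervention in two incompatible ways, and the methods statement, read literally, is the more severe. The readings differ by 30% of energy needs, or 1.86-fold in both calories supplied and deficit, whatever the body size. The kcal figures are illustrations that rest on assumed heights and BMIs and on the 30–60 y equations.

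The contradiction itself is certain. That 65% of needs was intended is probable, not proven. Sample size, power and the ANOVA are unaffected. Because the sentence sets what participants are prescribed to eat for six weeks, it should be corrected before use and not left as a typographical matter.

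**What to change.** The investigators should first confirm the intended value. If it is the summary's, the D.4 sentence should read: *The obese UF group will be assigned a diet 35% less than (i.e. 65% of) the calculated energy needs.* The summary and the kitchen instructions should use the same wording, giving both forms of the percentage. If 35% of needs was intended, the summary must change and section 8.3.e must address very low intake.

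The cost for the expected case is a protocol wording amendment, with no change to sample size, power or analysis.

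Two minor points in section D.4 can be tidied in the same amendment:

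- The run-in rule is "If their weight changes by 2%, their caloric intake will be adjusted by 200 kcal accordingly", while Baseline Visit 2 says "Adjust calories by 2%, if needed". The second should say to adjust by 200 kcal if weight has changed by 2%.
- Section D.1 admits "Non-diabetic individuals aged 18-70 years who are in good health", but the printed equations stop at 60 years. The equation for ages 61–70 should be given.

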- Ecological Momentary Assessment (EMA) using Smart-phones: participants will use Smart-phones to monitor adherence. In brief, EMA research techniques reflect repeated, real-time (momentary) assessment in the participants' typical environment (48). Recent studies have shown that anger predicted binge episodes ([name] et al., 2007) and overall negative moods were higher on binge days than on non-binge days (Wegner et al., 2002). Signal contingent recordings will be used, which involves respondents recording experiences whenever signaled at semi-random times throughout the day. Signals will occur two times/day: once between 8am and 3pm and once between 3pm and 9pm and will be randomly dispersed.

When signaled, volunteers will be asked:

- Since the last time you were signaled, have you eaten anything?
- If yes, did you eat the study food provided to you?
 - If yes, did you finish the food?
 - If no, which foods didn't you eat?
- Did you eat anything else (in addition to the food provided)?
 - If yes, what did you eat?
- Mood will be assessed using the short version of the Positive and Negative Affect Scale (PANAS, Watson & Clark, 1989). Each item will be rated on a 7-point scale (0, none; 3 moderately; 6 extremely; [name] 2007; Wegner et al., 2002)
- Phones will have a data service plan to allow for transfer of data from the phone to a stored network. GPS and/or other tracking systems will not be installed and volunteers will not be monitored or tracked via the smart phone. Participants will have the option of using their own smart phones if they already have one.

After completion of the 6-wk outpatient study, volunteers will repeat the following tests during their final outpatient visit:

Post-Intervention Visit:

- weight, blood pressure
- Lab work; CBC, Research chemistry profile, urine HCG (for females)
- Repeat DXA
- Repeat behavioral measures and psychological performance tests
- Final adherence measurement and exit interview

5. Patient monitoring:

5.1 Criteria for individual subject withdrawal:

Any subject experiencing (1) clinically apparent deterioration or severe side effects resulting from the dietary interventions or (2) who develops any medical problem that poses a safety risk for further participation will be withdrawn.

6. Data Analysis and Sample Size:

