 - a. *Completion of recall*: adherent = completed recall; non-adherent = did not complete recall
 - b. *Dietary Adherence to Foods provided*: adherent = consumed all; non-adherent = did not consume all
 - c. *Adherence to Additional Foods*: adherent = did not consume any; non-adherent = consumed additional foods
6. EMA recordings: there will be two contacts per day. For each contact there will be three adherence scores. To avoid having EMA be more heavily weighted in the total score, the total weekly score will be divided by 7 to obtain an average weekly EMA score (42 possible total points per week; 6 possible total average points):

- a. *Completion of recording*: adherent = completed recording; non-adherent = did not complete recording. We will define incomplete or missing entries as non-adherent for that day.
 - b. *Dietary Adherence to Foods provided*: adherent = consumed all; non-adherent = did not consume all
 - c. *Adherence to Additional Foods*: adherent = did not consume any; non-adherent = consumed additional foods
7. Additional Non-Intervention Related Adherence Measure (once per week. For each rating there will be 1 score (6 possible total points over the study): We will also track the arrival time for weekly counseling session as a measure of adherence that is not directly related to the study intervention. Appointment adherence will be scored as the arrival within 5 minutes of the scheduled time and actual arrival time will be documented as a continuous measure of adherence. This measurement will allow us to examine the relationship between adherence to the dietary protocol and adherence to "other" factors (e.g. punctuality) and it will be included in the total adherence score.
- a. Appointment adherence: adherent = arrived within 5 minutes of scheduled appointment; non-adherent = did not arrive within 5 minutes of scheduled appointment

Adherence Score: The above variables will be totaled up to calculate a total adherence score out of a possible 21 points during each week. A percent (%) adherence score will also be calculated by dividing the total score by the number of variables assessed (21) and multiplying by 100 ($[(\text{total}/21)*100]$).

Statistical Analysis:

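### The EMA prompts do not reliably collect what item 6b scores: a contact with nothing eaten has no defined score, and a skipped study meal can be credited as eaten.

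*Combined protocol and SAP*

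**What the plan says.** Under Outpatient Adherence Contacts, the EMA script opens with "Since the last time you were signaled, have you eaten anything". A yes leads to "If yes, did you eat the study food provided to you", and a further yes to "If yes, did you finish the food". A line for the negative answer follows: "If no, which foods didn't you eat". A separate question then covers food other than the study food. On timing, the section states: "Signals will occur two times/day: once between 8am and 3pm and once between 3pm and 9pm".

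In section 6, Measuring Adherence, item 6b scores every contact with the rule "adherent = consumed all; non-adherent = did not consume all". The same wording is used for the diary and the three 24-hour recalls (items 2b to 5b). For EMA the weekly weight is "42 possible total points per week; 6 possible total average points". Item 6a adds: "We will define incomplete or missing entries as non-adherent for that day". The total out of 21 per week is the basis of the dependent variable in the primary one-way ANOVA. No section says which combination of prompt answers produces a 0 or a 1 on item 6b.

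**The concern.** Item 6b needs one fact per contact: was all the supplied food for that interval eaten? No prompt puts that question to every participant. The script first asks about eating in general, then about study food, then about finishing it, so whether a skipped meal comes to light depends on the path taken and on how the participant understands the words.

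Item 6b feeds the primary endpoint, and the total adds it to items 2b to 5b as if all five measured the same behaviour. If the prompts do not collect the answer, it cannot be rebuilt afterwards from the EMA record.

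**Working it through.** **1. Follow each answer path to item 6b.**

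| Answers at a contact | What is learned about supplied food | Item 6b score in the plan |
|---|---|---|
| Nothing eaten | Nothing; the study-food prompts hang on a yes | Not defined |
| Ate, but no study food | Study food was not eaten | 0 is the natural reading |
| Ate study food, did not finish | Some was left | 0 is the natural reading |
| Ate study food, finished | Depends on what the food refers to | 1 is the natural reading |

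The first row is ambiguous in substance. Nothing eaten may mean that a meal was skipped, or that none was due. Scoring it 1 credits a skipped meal; scoring it 0 penalises someone who had nothing to eat yet.

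The last row has two readings. If the food means all the study food provided, a person who finished breakfast and skipped lunch answers no. If it means the food that was eaten, the same person truthfully answers yes. The extracted layout does not show whether the line on uneaten foods follows a no to the study-food prompt or a no to the finishing prompt. Either way, yes to both never reaches it.

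**2. Does one contact cover more than one meal?** From the stated windows:
- First to second signal on the same day: from almost 0 hours (both close to 3pm) up to 13 hours (8am to 9pm).
- Second signal to the next day's first: from 11 hours (9pm to 8am) up to 24 hours (3pm to 3pm).

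Table 2 shows four eating occasions a day against two signals. An interval can therefore hold several study meals or none, so both problem paths can arise in ordinary use.

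**3. Weight in the score.**
- Maximum weekly score: 2 (attendance) + 4 × 3 (diary and three recalls) + 42/7 (EMA) + 1 (punctuality) = 21, as stated.
- Item 6b: 2 contacts × 7 days / 7 = 2 points, and 2/21 = 9.5% of the total.
- One contact: 1/7 = 0.14 point, or 0.7% of the total.
- Points for consuming all supplied food: 4 from the diary and recalls + 2 from EMA = 6, so EMA carries one third.

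**4. What this could do to the primary comparison.** Inputs from Power Calculation and Table 3A: means 13, 16 and 19, SD 6, 20 per group, alpha 0.05. The noncentrality is λ = n × Σ(mean − grand mean)² / SD² = 20 × 18 / 36 = 10. The exact noncentral F gives power 0.793, which reproduces the plan's figure.

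The documents give no rate of false credit. The rows below are assumptions that show how the result depends on the pattern across groups, with SD held at 6.

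| Assumed false credit | Means | λ | Power |
|---|---|---|---|
| Equal in all groups (+0.5) | 13.5 / 16.5 / 19.5 | 10.00 | 0.793 |
| Obese UF only, +0.14 | 13.14 / 16 / 19 | 9.53 | 0.773 |
| Obese UF only, +0.5 | 13.5 / 16 / 19 | 8.43 | 0.717 |
| Obese UF only, +1.0 | 14 / 16 / 19 | 7.04 | 0.633 |
| Obese UF only, +2.0 (ceiling) | 15 / 16 / 19 | 4.81 | 0.466 |
| Lean WMEN only, +0.14 | 13 / 16 / 19.14 | 10.48 | 0.813 |
| Lean WMEN only, +0.5 | 13 / 16 / 19.5 | 11.76 | 0.858 |
| Every item 6b miss credited, miss rate = 1 − mean/21 | 13.76 / 16.48 / 19.19 | 8.19 | 0.704 |

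The last row adds 2 × (1 − mean/21) to each mean. An equal shift changes nothing. An unequal one can narrow or widen the differences, depending on the group in which skipping goes unrecorded more often.

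**The case against.** The strongest reply is that the script does ask about uneaten food. It asks whether the provided study food was eaten and which foods were not, and the natural antecedent of the food is the study food provided. On that reading a skipped lunch produces a no. Item 6b also plainly gives 0 when not everything was consumed. The worked score sheet shows the item losing points: 6 of 7 and 5 of 7 on foods supplied, with the 6 arising in a week when all seven first contacts were completed. The rule on incomplete entries pulls EMA scores down, not up. Four other instruments cover the same behaviour.

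Much of this stands. A reader might infer that skipping a study meal earns full points on this item. The documents do not support that: one of the two readings gives a no, and the path with nothing eaten is unscored, not credited. A reader might also infer that the diary and recalls would score the same day 0. Each recall covers only 24 hours once a week and the diary yields one such point a week, so the instruments were never matched day by day. Nor can a shift in score level be set directly against the planned 3-point difference, because an equal shift leaves that difference unchanged.

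The reply does not remove the gap. The score sheet does not say why points were lost, so it does not show that a meal skipped alongside a finished one is caught. The rule on incomplete entries does not clearly cover a completed entry that reports nothing eaten. The outcome still depends on how each participant reads two words.

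**Conclusion.** The concern holds in a limited form. The script leaves item 6b without a defined score when nothing was eaten, and it allows a skipped study meal to be credited when another was finished. Up to 2 of the 21 weekly points are exposed, at 1/7 point per contact.

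The documents do not show that the primary score is inflated overall or that the comparison is biased in a known direction. They give neither a rate of skipped meals nor a reason to assume one pattern across groups. The power figures from 0.466 to 0.858 are illustrations on assumed rates, and the lowest requires all 2 points to be credited in error in the obese UF group alone. For the comparison of means the gap matters mainly if skipping differs between groups.

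It is still more than a missing detail, because an answer that was not collected at the signal cannot be recovered at analysis.

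**What to change.** At every signal, including after a report of nothing eaten, ask one question such as: Of the study food you were due to eat since your last signal, was any skipped, left or thrown away? If yes, which? Score item 6b as 0 for yes and 1 for no, and write that rule into Measuring Adherence.

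The question must exclude food not yet due. Meals are taken home and signals come at semi-random times, so without that limit a meal planned for later could be reported as skipped. Participants need a short instruction on what counts as due.

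The cost is a change to the smart-phone script before enrolment and one extra question for participants who report having eaten nothing.
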